Study Protocol

Efficacy of Therapeutic Plasma Exchange Adsorption Diafiltration(PEAF)
for Septic Shock With Multiple Organ Dysfunction Syndrome in intensive care unit:
A Multicenter,Open-Parallelled ,Randomized and Controlled Clinical Trial

Original Protocol : May 18,2018

Principal Investigator

[name] MD PhD

Sponsor

Shenzhen Second People's Hospital

Investigators and Institutional Review Board

Principal Investigator

[name] MD PhD

Other Investigators

School of Public Health, Southern Medical University

[name]

[name]

Institutional Review Board

The IRB

Background

Septic shock with multiple organ dysfunction syndrome (MODS) is a life-threatening clinical condition due to coagulant disorder immunoparalysis to infection. For this reason the extracorporeal therapies for the treatment of septic shock with MODS have become widespread in the ICU and, at the same time, new extracorporeal depurative techniques have been developed for the removal of inflammatory mediators. One of these techniques is therapeutic plasma exchange (TPE) that remove pathologically elevated cytokines and simultaneously to replace protective plasmatic factors. other techniques is CPFA (coupled plasma-filtration adsorption) that uses a sorbent once the separation between plasma and blood has been obtained with a plasma filter. The others is Plasma dialysis filtration(PDF) that can remove inflammatory mediators for patients with multiple organ dysfunction syndrome.

Aims and Goals

The current protocol is to evaluate the effect of Therapeutic Plasma Exchange Adsorption Diafiltration (PEAF) on Septic shock with multiple organ dysfunction syndrome (MODS).

Setting and design

This is a open-parallelled ,randomized and controlled clinical trial and the study is endorsed by Health and Family Planning Commission of Shenzhen Municipality and Shenzhen Second People's Hospital, and is approved by Medical ethics committee of Shenzhen No.2 People's Hospital.

According to the mortality rate of patients with sepsis combined with MODS in our hospital for about one year is about 40%. The literature reported that the OR of coupled plasma-filtration adsorption(CPFA)treatment group was 0.36 (according to $\alpha=0.05$, unilateral, $1-\beta=0.8$; $n=152(76\times 2)$), according to statistical principles, The sample size calculated by PASS11.0 requires at least 152 cases, an increase of 10% of shedding cases. the total number of cases is at least 168 subjects finally.

	Sample Size Grp 1	Sample Size Grp 2	Prop H1 Grp 1 or Trtmnt P1	Prop Grp 2 or Control P2	O.R. if H0 OR0	O.R. if H1 OR1	Target Alpha	Actual Alpha	Beta
Power	N1	N2	P1	P2	OR0	OR1	Alpha	Alpha	Beta
0.8041	76	76	0.1935	0.4000	1.000	0.360	0.0250	0.0259	0.1959

Methods:

The patients are considered registered once the informed consent form has been obtained by the patient or legal representative. The recruitment process ends with the patient center randomisation. Patients will be divided randomly into two arms (control and intervention).

The characteristics of the groups are: Control group: Treatment following the suggestions provided by the recent surviving sepsis guidelines, as well as standard care guidelines typically followed in China. HVHF, High volume hemofiltration for septic shock with MODS is permitted in Control group routinely (Blood pump: 200ml/min, replacement fluid pump 45ml/kg/min, dialysate pump 45ml/kg/min, waste pump 90ml/kg/min, and high-volume hemofiltration for 16 hours with ACF180™ AsahiKASEI or AV1000S™ Fresenius)

Intervention group: the patient is placed in the PEAF group, he/she will receive treatment with PEAF immediately after randomization. PEAF that is TPE (therapeutic plasma exchange 20ml/kg/d Fresh frozen plasma, Blood pump: 120ml/min, replacement pump 20ml/kg/min, dialysate pump 0ml/kg/min, waste pump 20ml/kg/min, plasma exchange 1 hour) plus PFA (Blood pump: 120ml/min, Plasma separation rate 25-30%, plasma-filtration adsorption with Mediasorb™ BELLECO ITALY

≥30ml/min) and HVPDF(High volume plasma diafiltration with ACF180™ AsahiKASEI or Ultraflux AV1000S™ Fresenius , Blood pump same as PFA , replacement fluid pump 2000ml/h, dialysate pump 2000ml/h, waste pump 4000ml/h),with PFA and HVPDF for 15 hours in the first 3 days. Same protocol with control group after 3days.

The scheme of the trial is displayed in figure 1 and figure 2

[figure not shown]

Figure 1: Study diagram

[figure not shown]

Figure 2: Pipeline connection

Variables and measurements

The primary outcome is all-cause mortality assessed at 28 days from the recruitment of the patient.

Moreover, at the descriptive level and in order to check the homogeneity of both groups, the following variables will be collected at the time of recruitment: birth year, gender, height, dry weight, body temperature, heart rate, blood pressure, count blood cell, glucose level, plasma creatinine, bilirubinaemia, plasma C reactive protein, procalcitonin level, blood gas analysis, lactate, urinary output(mL/kg/hours), arterial oxygen tension/fractional inspired oxygen ratio, International Normalized Ratio(INR),Prothrombin time(second),activated partial thromboplastin time(second),Fibrinogen(g/L),D-Dimer(mg/L),Organ function(Acute Physiology and Chronic Health Evaluation II, Sequential Organ Failure Assessment, The Confusion Assessment Method for The Intensive Care Unit).

Secondary Outcome: all-cause mortality within 90 days from randomization ,free hours of vasoactive drugs after randomization within 14 days.

Finally, for all patients enrolled in the study, 10 ml of whole blood was taken from 8 am to 10 am every day, After centrifugation, the plasma was stored in a negative 80-degree refrigerator for subsequent follow-up testing.

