## Statistical Analysis Plan

Patients will be divided into control or intervention with center randomisation. Full Analysis Set (FAS): Analyzes all cases that were randomized into clinical trials. The shed data was estimated using the LOCF method. Per Protocol Set(PPS): Analysis of all cases that meet the test plan, good compliance, no banned drug use during the trial, and complete the contents of the CRF regulations. The efficacy analysis of this trial was simultaneously analyzed using the full analysis set and the compliance set. The entire analysis will be undertaken with “the intention-to-treat” principle, even though we have foreseen a “by protocol” analysis. only patients who have received at least the minimum established doses of PEA treatment in the experimental arm will be evaluated.

The descriptive analysis will be performed using means and SDs for quantitative variables and absolute and relative frequencies for qualitative variables. To verify the homogeneity of both groups,  $\chi^2$  (Pearson or Fisher) and t-test will be used. To determine the benefit of our intervention, the clinical relevance indicators will be calculated: relative risk, absolute risk reduction, relative risk reduction, number needed to treat.

Specific analysis method:

1. Statistical descriptions were performed for the cases of rejection and shedding and for pretreatment data, Pearson  $\chi^2$  test was used for all-cause mortality within 28 and 90 days.
  2. Pearson  $\chi^2$  test or exact probability calculation, t-test or analysis of variance and non-parametric test were performed for other outcomes.
  3. the central effect CMH method was performed for the comparison of the clinical efficacy of the two groups, and the qualitative or ordinal variables are analyzed by using the GEE method.
  4. A statistical description method was used for adverse reactions. Chi-square or Fisher exact test were used for the incidence of adverse reactions between groups.
  5. Survival analysis: Cox survival curve; multivariate analysis: unconditional logistic regression;
- All analyses will be performed with a significance of 5% and the associated CI of each relevant parameter will be calculated. The statistical software used will be IBM SPSS Statistics V.22.

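### The sample-size text states a one-sided alpha of 0.05, but its own PASS output used 0.025, the level that matches the SAP's 5% Pearson chi-square test

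*Protocol*

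**What the plan says.** Protocol, sample-size paragraph (under Setting and design). Control mortality "in our hospital for about one year is about 40" percent, and the odds ratio reported for the CPFA "treatment group was 0.36". The error rates are given as "according to $\alpha=0.05$, unilateral, $1-\beta=0.8", with 152 patients (76 per arm), raised to 168 for dropout. The text adds: "The sample size calculated by PASS11.0 requires at least 152 cases".

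Protocol, PASS output below that paragraph. The row shows power 0.8041, 76 and 76 patients, mortality of "0.1935 0.4000" (treatment, control), and an odds ratio of 0.360. Its last three entries, target alpha, actual alpha and beta, are "0.0250 0.0259 0.1959". The row prints no side.

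SAP, Specific analysis method. Item 1 says that the Pearson chi-square "test was used for all-cause mortality within 28 and 90 days". The last bullet says "All analyses will be performed with a significance of 5" percent. The SAP does not say whether that level is one-sided or two-sided.

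**The concern.** The sentence and the table beneath it give different error rates for one calculation, and nothing elsewhere in either document reconciles them. The sentence is also the only explicit statement of sidedness in the two documents. An analyst who turned to the protocol to settle the SAP's silence would find one-sided 0.05.

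The primary outcome is 28-day mortality in an open-label trial. If the one-sided reading reached the analysis, for example by halving the chi-square p-value, PEAF could be declared beneficial at about twice the false-positive rate used to size the trial. No passage proposes doing this, so the risk is conditional.

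**Working it through.** **Inputs.** Control mortality p2 = 0.40, odds ratio 0.36, power 0.80 and 1:1 allocation, all from the protocol's sample-size paragraph and PASS row.

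**Treatment mortality.** Odds = 0.36 × 0.40/0.60 = 0.24, so p1 = 0.24/1.24 = 0.1935. This matches the PASS row.

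**Sample size at each alpha.** The pooled z formula is

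n per arm = [z(α)·√(2·p̄(1−p̄)) + z(β)·√(p1(1−p1) + p2(1−p2))]² / (p2−p1)²

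with p̄ = (0.1935 + 0.40)/2 = 0.2968, p2−p1 = 0.2065, first root 0.6461, second root 0.6294 and z(β) = 0.8416.

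- One-sided 0.025 (z = 1.960): [(1.960 × 0.6461 + 0.8416 × 0.6294)/0.2065]² = 75.7, so 76 per arm and 152 in total. This is the plan's figure. Adding 10% gives 152 × 1.10 = 167.2, rounded up to 168.
- One-sided 0.05 (z = 1.645): [(1.645 × 0.6461 + 0.8416 × 0.6294)/0.2065]² = 59.5, so 60 per arm and 120 in total.

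Other one-sided 0.05 formulas do not reach 76 either: unpooled variance gives 58, the log odds ratio 63, and the continuity correction 69.

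**Exact check at 76 per arm.** Summing binomial probabilities over all outcomes of the one-sided pooled z test gives:

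| Nominal one-sided level | Power | Exact size, common mortality 19.35% to 40% |
|---|---|---|
| 0.025 | 0.8041 | 0.0255 to 0.0268 |
| 0.05 | 0.8790 | 0.0505 to 0.0516 |

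The first row gives the printed power. With the variance multiplied by N/(N−1), its size at 40% mortality is 0.0259, which is the printed actual alpha. The 0.05 row matches neither figure.

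**What the SAP's test implies.** A Pearson chi-square test at 5% rejects above 3.84 = 1.96² in either direction. In the direction that favours PEAF it therefore works at 2.5%, the PASS level.

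**What a one-sided 5% reading would change.** This uses 84 per arm (168/2) and assumes 34 control deaths, about 40% of 84. The 34 is an illustration and not a figure in the documents.

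| PEAF deaths | Chi-square | p (Pearson) | p halved |
|---|---|---|---|
| 22/84 | 3.86 | 0.0495 | 0.025 |
| 23/84 | 3.21 | 0.073 | 0.037 |

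Under the test as written, 22 deaths pass and 23 fail. Under a one-sided 5% rule, 23 also pass. By exact enumeration at 84 per arm:

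- With 40% mortality in both arms, the false-positive rate in favour of PEAF is 0.0248 at one-sided 0.025 and 0.0494 at one-sided 0.05.
- Under the assumed effect, power is 0.8460 and 0.9097. The difference, 0.9097 − 0.8460 = 0.0637, means that about 6.4% of trials would fall between the two thresholds.

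**The case against.** The strongest reply is that nothing in the trial changes. The PASS row discloses every input, so a reader can reproduce 152 from it. The SAP's test already works at the stricter level, and no passage tells anyone to halve a p-value. On this view, one sentence misdescribes a correct calculation. That is a reporting inconsistency with no demonstrated consequence. Much of this stands: the PASS arithmetic is right, the sample size is sound, and the false-positive figures apply only under a reading that the SAP does not adopt. But the row only exposes the conflict. The sentence says something else, and it is the only place where a side is named.

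A second point also stands. The documents do not settle which half of the pair is wrong. The author may have meant 0.025 one-sided, or 0.05 two-sided; the 0.05 itself matches the SAP's 5%. The two repairs are equivalent for the sample size, so the wording of the fix should cover both.

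Third, the SAP's side is inferred from the test and not stated. The inference is firm for the Pearson chi-square. It does not show what was intended for the other analyses under the same 5% sentence, such as the t-tests, Cox and logistic models. That is a further reason to write the side down.

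**Conclusion.** The concern holds. The stated one-sided alpha of 0.05 contradicts the PASS row, and the printed 76 per arm, power of 0.8041 and actual alpha of 0.0259 all follow from one-sided 0.025. On the stated inputs about 60 per arm would be enough, or 76 per arm would have 87.9% power. That the sentence, and not the table, is at fault is very likely but remains an inference. It rests on the reproduced figures and on the Pearson chi-square being non-directional.

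The trial is not undersized. This should be fixed because it misstates the error rate of the primary comparison, although the harm arises only if the one-sided wording is applied in the analysis.

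**What to change.** In the protocol's sample-size paragraph, replace the one-sided alpha of 0.05 with a two-sided alpha of 0.05 (one-sided 0.025). This covers either possible slip and is the level at which the PASS row gives 76 per arm and 80.4% power. In the last bullet of the SAP's Specific analysis method, state a two-sided significance level of 5% with 95% confidence intervals. For the mortality outcomes this spells out what the Pearson chi-square test already implies. For the other analyses it is a choice that the sponsor should confirm.

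The cost is one line in each document. The 152 patients, the 168 with dropout, the 80.4% power and the primary test are unchanged.

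### The control-arm HVHF fluid rates, given in ml/kg/min, are out of scale with the blood pump rate stated beside them, so the comparator dose is undefined as written.

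*Protocol*

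**What the plan says.** The protocol's Methods section, control group paragraph, allows HVHF as a routine addition to guideline care. It gives the settings as "Blood pump: 200ml/min, replacement fluid pump 45ml/kg/min, dialysate pump 45ml/kg/min, waste pump 90ml/kg/min", and the session as "high-volume hemofiltration for 16 hours with ACF180™ AsahiKASEI or AV1000S™ Fresenius". The blood pump rate is absolute, whereas the three fluid rates are per kilogram per minute.

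The intervention group paragraph describes high volume plasma diafiltration (HVPDF) on the same two filters, at "replacement fluid pump 2000ml/h, dialysate pump 2000ml/h, waste pump 4000ml/h". The blood pump is as for plasma-filtration adsorption, which is 120 ml/min. HVPDF runs for 15 hours in the first 3 days. The paragraph ends with "Same protocol with control group after 3days", so the HVHF settings also apply to PEAF patients from then on.

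The plasma exchange (TPE) step in the same paragraph also uses ml/kg/min: 20 for replacement, 0 for dialysate and 20 for waste, for one hour, with a 120 ml/min blood pump. The same parenthesis states a plasma volume of 20 ml/kg per day.

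Neither the protocol nor the SAP gives a conversion, a weight cap or another unit for the HVHF rates. Dry weight is collected at recruitment (Variables and measurements), but no value or expected range is stated.

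**The concern.** HVHF is the only extracorporeal treatment specified for controls, and PEAF patients move to the control protocol after day 3. If its rates cannot be reconciled with the blood pump on the same circuit, the protocol does not define the comparator for 28-day mortality. A site would have to decide for itself what was meant, and sites might decide differently. A trial report could not then state what the protocol dose was.

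There is also a consequence for the analysis sets. The SAP's per protocol set requires that a case meets the plan with good compliance. For HVHF, compliance cannot be judged against rates that do not fit their own circuit.

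**Working it through.** **Inputs.** From the control group paragraph: "Blood pump: 200ml/min", "replacement fluid pump 45ml/kg/min", "dialysate pump 45ml/kg/min", "waste pump 90ml/kg/min", 16 hours. From the intervention group paragraph: HVPDF at 2,000, 2,000 and 4,000 ml/h with a 120 ml/min blood pump; TPE at 20 ml/kg/min for 1 hour, 20 ml/kg per day, 120 ml/min blood pump. Body weight is an assumption, taken as 40 to 100 kg.

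**1. Do the fluid rates agree with each other?** Waste = replacement + dialysate.
- HVHF: 45 + 45 = 90 ml/kg/min, as stated.
- HVPDF: 2,000 + 2,000 = 4,000 ml/h, as stated.
- TPE: 20 + 0 = 20 ml/kg/min, as stated.

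All three balance, so the sums are not at fault.

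**2. Do the HVHF fluid rates fit the blood flow?** Rate (ml/min) = rate per kg × weight; ratio = rate / 200.

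| Assumed weight | Replacement | Ratio | Waste | Ratio |
|---|---|---|---|---|
| 40 kg | 45 × 40 = 1,800 ml/min | 9.0 | 90 × 40 = 3,600 ml/min | 18 |
| 60 kg | 2,700 ml/min | 13.5 | 5,400 ml/min | 27 |
| 100 kg | 4,500 ml/min | 22.5 | 9,000 ml/min | 45 |

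The weight at which the fluid rate equals the blood flow is 200 / 45 = 4.4 kg for replacement and 200 / 90 = 2.2 kg for waste. The result does not depend on which adult weight is assumed.

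Over a 16-hour session, blood through the circuit is 200 × 60 × 16 / 1,000 = 192 L. Waste at 60 kg is 5,400 × 60 × 16 / 1,000 = 5,184 L. The range is 3,456 L at 40 kg to 8,640 L at 100 kg.

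**3. Is the HVPDF prescription coherent with its own blood pump?** Waste is 4,000 / 60 = 66.7 ml/min, and 66.7 / 120 = 0.56 of the blood flow. Here the fluid rates and the blood flow are on the same scale.

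**4. How far apart are the two prescriptions?** HVHF replacement is 1,800 × 60 = 108,000 ml/h at 40 kg and 4,500 × 60 = 270,000 ml/h at 100 kg. Divided by 2,000 ml/h, this is 54 to 135 times the HVPDF rate. Waste gives the same ratios, because both terms double.

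**5. Does the same unit cause trouble elsewhere?** TPE at 20 ml/kg/min for 60 minutes is 20 × 60 = 1,200 ml/kg. Against 20 ml/kg per day that is 1,200 / 20 = 60 times. At an assumed 60 kg it is 72 L against 1.2 L, and the pump rate of 20 × 60 = 1,200 ml/min is 10 times the 120 ml/min blood pump. From 40 to 100 kg the ratio to blood flow is 6.7 to 16.7.

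**The case against.** The strongest reply is that this is an obvious slip in a unit, which any intensive care team would correct without harm. The planned mortality test and the sample size calculation do not use these figures. The second part stands: the damage is to the definition and reproducibility of treatment, not to the test or its power. The first part does not settle the matter. The documents do not say which element is the slip, and the size of the between-arm contrast in filtration depends on how it is resolved. The unit also recurs in the TPE parenthesis, so it cannot be dismissed as one isolated keystroke.

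A reader might draw several stronger conclusions, which the documents do not support:

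- **That the two arms' rates contradict each other because the filters are the same.** HVHF and HVPDF are different modalities with different blood flows (200 and 120 ml/min), and their rates may properly differ. The 54- to 135-fold gap supports a unit or scale error but is not itself a contradiction.
- **That the four control-arm figures all disagree.** The three fluid rates balance; only their relation to the blood pump fails.
- **That the blood pump figure is the correct one.** The text shows that the figures do not fit together, not which of them is wrong.
- **That the dose is physically undeliverable, or that patients were endangered.** No pump limit is given. The finding rests on the ratio to blood flow and the session volumes.
- **That centres used different doses.** This is a risk that the text creates, not something it shows.
- **That every control patient was to receive HVHF.** The wording permits it routinely, which leaves that open.

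The two figures (study diagram and pipeline connection) are not available here and may state rates. That would not remove the conflict in the text.

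**Conclusion.** The point holds as a unit or scale inconsistency between the control-arm HVHF fluid rates and the blood flow in the same parenthesis, and the text is wrong as written. At an assumed 40 to 100 kg, replacement is 9 to 22.5 times and waste 18 to 45 times the blood flow. Only the multiples depend on the assumed weight; the existence of the conflict does not at any adult weight.

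Because the after-day-3 sentence carries these settings into the PEAF arm, the HVHF dose is undefined in both arms wherever it is used. Variation between centres and a safety risk from literal copying are possible consequences, not demonstrated ones. The TPE parenthesis has the same kind of problem, with a 60-fold internal discrepancy that needs no weight assumption.

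**What to change.** The investigators should:

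1. Reconcile the control-arm replacement, dialysate and waste rates with the stated blood flow.
2. Check the ml/kg/min figures in the TPE parenthesis at the same time, against both the daily plasma volume and the blood pump rate there.
3. Express the effluent rates of both arms in one common unit, so that the intended contrast can be seen.
4. Make the after-day-3 sentence refer to the reconciled text.
5. Notify the sites.
6. If patients have already been treated, document by centre the rates actually delivered. The documents give only the date of the original protocol (18 May 2018), so the state of recruitment is not known from them.

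Which figure or unit is right is for the investigators to decide.

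The cost is a short protocol correction and a notice to sites, with no extra patients or procedures. Step 6, if needed, adds the work of collecting delivered rates from treatment records.

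### The TPE pump rates give 60 times the plasma dose stated beside them, and the HVHF rates cannot be delivered as written, so their unit needs confirming

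*Protocol*

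**What the plan says.** All the settings are in the Methods section of the protocol.

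- **TPE, intervention arm:** "therapeutic plasma exchange 20ml/kg/d Fresh frozen plasma, Blood pump: 120ml/min, replacement pump 20ml/kg/min, dialysate pump 0ml/kg/min, waste pump 20ml/kg/min, plasma exchange 1 hour". Dose, pump rates and duration stand together in one parenthesis.
- **HVHF, control arm:** "Blood pump: 200ml/min, replacement fluid pump 45ml/kg/min, dialysate pump 45ml/kg/min, waste pump 90ml/kg/min", run for 16 hours on one of two named filters. No total or hourly dose is given.
- **HVPDF, intervention arm:** "replacement fluid pump 2000ml/h, dialysate pump 2000ml/h, waste pump 4000ml/h", on the same two filters. It runs together with PFA for 15 hours, and its rates are per hour and not scaled to weight.

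HVHF reaches both arms. In the control arm, "High volume hemofiltration for septic shock with MODS is permitted in Control group routinely"; for the intervention arm the text says "Same protocol with control group after 3days". Nothing else in the visible protocol or the SAP restates or corrects the per-minute units. The protocol also says "The scheme of the trial is displayed in figure 1 and figure 2"; neither figure is available, and whether they carry flow rates is unknown.

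**The concern.** The TPE sentence gives a dose, a rate and a duration, so the three can be checked against each other, and they do not agree. The HVHF entries use the same unit and lead to flows far above the blood pump rate given beside them.

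These are operative device settings in a trial described as multicentre. For TPE, a careful reader can work back to the right rate from the dose and the duration. For HVHF there is no stated dose to work back from, so two centres could correct the obvious error in different ways and prescribe different intensities of haemofiltration. That would leave part of the comparator, and part of the intervention arm's care after day 3, undefined. The documents show no misdelivery and no harm.

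**Working it through.** **Inputs.** From the protocol, Methods: TPE dose 20 ml/kg/d, blood pump 120 ml/min, replacement and waste 20 ml/kg/min, dialysate 0, 1 hour. HVHF blood pump 200 ml/min, replacement 45, dialysate 45 and waste 90 ml/kg/min, 16 hours. HVPDF waste 4,000 ml/h. Body weight is not given; I assume 60 kg, with a range of 50 to 80 kg.

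**TPE: dose = rate × duration**

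- As written: 20 ml/kg/min × 60 min = 1,200 ml/kg. Against the stated dose, 1,200 / 20 = 60. Weight cancels, so the ratio needs no assumption.
- Flow check: dialysate is zero, so all the waste is removed plasma. Waste at 20 ml/kg/min passes the 120 ml/min blood flow at any weight above 120 / 20 = 6 kg.
- Could the duration be the error? At 20 ml/kg/min the stated dose would be reached in one minute. One hour of TPE plus 15 hours of PFA and HVPDF also makes 16 hours, the same as control-arm HVHF. The duration therefore looks right and the unit wrong.
- Read as ml/kg/h: 20 × 1 h = 20 ml/kg, the stated dose at every weight.
- Read as ml/min: 20 × 60 = 1,200 ml, which is 24, 20 and 15 ml/kg at 50, 60 and 80 kg. This matches only at 60 kg.

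The zero dialysate entry carries the same unit but has no numerical effect.

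**HVHF as written**

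- Replacement at 60 kg: 45 × 60 = 2,700 ml/min; 2,700 / 200 = 13.5 times blood flow (11.3 to 18 over 50 to 80 kg).
- Waste at 60 kg: 90 × 60 = 5,400 ml/min; 5,400 / 200 = 27 times blood flow (22.5 to 36).
- Waste includes dialysate, so blood flow is not a strict limit on it. Waste minus dialysate is 90 − 45 = 45 ml/kg/min, and this alone passes 200 ml/min above 200 / 45 = 4.4 kg.
- Waste over 16 hours at 60 kg: 5,400 ml/min × 960 min = 5,184 L.
- Against HVPDF waste on the same filters: 5,400 × 60 = 324,000 ml/h; 324,000 / 4,000 = 81 times (67.5 at 50 kg, 108 at 80 kg).

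**HVHF under the two readings that could be delivered**

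| | 50 kg | 60 kg | 80 kg |
|---|---|---|---|
| ml/kg/h: replacement, ml/h | 2,250 | 2,700 | 3,600 |
| ml/kg/h: replacement as share of blood flow | 18.8% | 22.5% | 30% |
| ml/kg/h: replacement over 16 h, L | 36.0 | 43.2 | 57.6 |
| ml/kg/h: waste relative to HVPDF | 1.13 | 1.35 | 1.8 |
| ml/kg/h: waste, ml/kg/h | 90 | 90 | 90 |
| ml/min: replacement, ml/h | 2,700 | 2,700 | 2,700 |
| ml/min: replacement over 16 h, L | 43.2 | 43.2 | 43.2 |
| ml/min: waste relative to HVPDF | 1.35 | 1.35 | 1.35 |
| ml/min: waste, ml/kg/h | 108 | 90 | 67.5 |
| ml/kg/h relative to ml/min | -17% | 0 | +33% |

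The last row is 2,250 / 2,700 − 1 and 3,600 / 2,700 − 1. Both readings give workable flows and agree only at 60 kg.

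**The case against.** The TPE contradiction is hard to dispute. The case on the other side concerns HVHF and the weight given to the whole point.

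- **HVHF contains no internal contradiction.** No dose is stated, the flows balance (45 + 45 = 90), no device limits are given, and waste over blood flow is a weak test. The HVPDF comparison shows a difference of scale, not a limit. This stands as a matter of logic: the HVHF part is an argument from scale. It does not rescue the rates, because net filtration alone exceeds blood flow in any plausible ICU patient, and the 16-hour volume runs to thousands of litres.
- **One slip, minute for hour, explains all six entries.** It keeps the weight scaling written each time and fits TPE exactly, whereas ml/min needs a stray per-kg term. This is a good reason to expect ml/kg/h, and it makes the -17% to +33% spread a possibility rather than a forecast. It is still an inference, because the same section also uses ml/min and ml/h.
- **HVHF is permitted, and the text does not say it is mandatory.** True, so these rates may not apply to every control patient. A treatment permitted as routine still needs a usable dose.
- **The slip reveals itself and touches no analysis, so it is minor.** No one could run these rates, and neither the primary outcome nor the SAP depends on them. I accept that there is no statistical consequence. I would still correct it, because these are treatment settings for critically ill patients and the HVHF dose cannot be recovered with certainty from the visible text.

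**Conclusion.** The concern holds, at two levels of certainty.

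- **TPE: proven.** The pump rates and duration give 60 times the stated daily dose at every weight, and ml/kg/h is the reading that reproduces that dose at every weight.
- **HVHF: not deliverable as written, intended unit unproven.** The size of the excess depends on the assumed weight, but the conclusion does not for ICU patients. The expected unit, ml/kg/h, rests on analogy with TPE and on the hourly HVPDF rates.

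Both statements cover the visible text only, since Figures 1 and 2 could not be seen. This should be fixed for treatment delivery and reproducibility.

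**What to change.** 1. **TPE:** change the pump units to ml/kg/h, giving replacement 20, dialysate 0 and waste 20 ml/kg/h for 1 hour, which equals the stated 20 ml/kg. The zero entry changes only for consistency.
2. **HVHF:** the sponsor should confirm the intended dose with the clinical and device leads, correct the unit (expected 45, 45 and 90 ml/kg/h), and state the resulting waste dose in ml/kg/h so that the text can be checked against itself.
3. **PFA and HVPDF:** leave as they are.
4. **Centres:** issue the corrected text to all sites, and check that the two figures agree with it.

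The cost is a short protocol correction (five entries with numerical effect plus the zero entry), one confirmation of dose, and a notice to sites. The sample size and the SAP do not change.

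### Vasoactive-free hours to day 14 has no rule for patients who die in the window, so the arm difference depends on an unstated scoring choice

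*Protocol*

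**What the plan says.** The protocol section on variables and measurements makes the primary outcome "all-cause mortality assessed at 28 days from the recruitment of the patient". Its secondary outcomes are 90-day mortality and "free hours of vasoactive drugs after randomization within 14 days". That phrase is the whole definition. It does not require the patient to be alive, gives no score for a death in the window, and does not say whether deaths are left out.

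The SAP puts all randomised cases in the full analysis set. Its only imputation rule is "The shed data was estimated using the LOCF method", and it does not say whether a death counts as shed data. Item 2 of the specific analysis methods offers a choice of tests: "t-test or analysis of variance and non-parametric test were performed for other outcomes". No composite, worst-rank or competing-risk method is attached to this outcome.

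The sample-size paragraph takes control mortality from experience "in our hospital for about one year is about 40" per cent. With an odds ratio for which the "treatment group was 0.36", its table puts intervention mortality at 0.1935.

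**The concern.** Drug-free hours in a fixed window are hard to interpret once patients can die in it. A dead patient receives no vasoactive drug, so a literal count credits every hour from death to day 14. A patient who dies on drug at 48 h would score 336 − 48 = 288 h, while a survivor who needed 96 h of drug scores 240 h.

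Death is the event PEAF is meant to reduce, and the plan expects it to be common and unequal between arms. The unstated rule could therefore decide the result. Analysts could follow the same text and score deaths as drug-free, score them as zero, or drop them, and reach different answers. The trial is open-label, so the choice should be fixed before outcome data are seen.

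**Working it through.** **1. The plan's own figure.** No figure is given for vasoactive-free hours, so the check is on the mortality inputs.

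- Control odds: 0.40/0.60 = 0.667. Times 0.36 = 0.24. Intervention mortality: 0.24/1.24 = 0.1935, as in the table.
- With the mean proportion 0.2968 and one-sided alpha 0.025, as in the table:
  n per arm = [1.96 × √(2 × 0.2968 × 0.7032) + 0.8416 × √(0.1935 × 0.8065 + 0.40 × 0.60)]² / (0.40 − 0.1935)² = 75.7, so 76 per arm.
- This agrees with the statement that the calculation "requires at least 152 cases". Then 152 × 1.10 = 167.2, rounded up to 168.

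**2. Assumptions not in the documents.**

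- The 40% and 19.35% are 28-day risks. The protocol does not give the time horizon of the 40%, but the calculation serves the 28-day primary outcome.
- A share s of these deaths falls by day 14: 70%, range 50–90%.
- Survivors in both arms average 96 h on drug, so PEAF has no effect on drug duration. Their score is 336 − 96 = 240 h (14 × 24 = 336).
- Early deaths occur at t hours, on drug throughout: 48 h, range 24–120 h.

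At s = 0.7 the 14-day death risks are 0.28 and 0.1355, a gap of 0.1445. The gap is 0.1032 at s = 0.5 and 0.1858 at s = 0.9.

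**3. Difference (PEAF minus control) by scoring rule.**

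- Death scores 0: gap × 240. The arm means are 0.72 × 240 = 172.8 h and 0.8645 × 240 = 207.5 h, so the difference is **+34.7 h** (+24.8 h at s = 0.5, +44.6 h at s = 0.9).
- Survivors only: 240 − 240 = **0 h**.
- Post-death hours count as free: a death scores 336 − t, so the difference is gap × [240 − (336 − t)] = gap × (t − 96).

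| t (h) | s = 0.5 | s = 0.7 | s = 0.9 |
|---|---|---|---|
| 24 | −7.4 | −10.4 | −13.4 |
| 48 | −5.0 | **−6.9** | −8.9 |
| 72 | −2.5 | −3.5 | −4.5 |
| 96 | 0 | 0 | 0 |
| 120 | +2.5 | +3.5 | +4.5 |

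**4. If LOCF of drug status were applied to deaths** (s = 0.7, t = 48).

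- All on drug at the last record: no free hours are added, so +34.7 h, the same as scoring death 0.
- All off drug for the last 30% of their time alive: each scores 336 − 0.7 × 48 = 302.4 h, and the difference is 0.1445 × (240 − 302.4) = −9.0 h.
- 30% of deaths off drug in this way: 0.1445 × (240 − 0.3 × 302.4) = +21.6 h.

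**5. Chance of a significant result favouring PEAF.** A Mann–Whitney simulation used 76 per arm, s = 0.7, deaths at around 48 h, and survivor time on drug drawn with mean 96 h. The chance was about 34% with deaths scored 0, about 1% with post-death hours counted as free (7–8% then significantly favoured control), and about 3% in survivors only.

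**The case against.** **LOCF.** A reader might infer that LOCF is what turns deaths into drug-free patients. The documents do not support that. The sample-size paragraph uses the same word for its dropout allowance ("an increase of 10% of shedding cases") beside a planned control mortality of 40%, so *shed* most naturally means dropout. No text applies LOCF to deaths, and carrying forward an on-drug status gives the same answer as scoring death 0. What remains is that LOCF, if applied, would make the score depend on the last record, so it is not a reliable cure.

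**Reversal.** A reader might infer that the literal count is biased against the arm with fewer deaths. The sign is that of t − 96, and the documents give neither time to death nor survivor time on drug. If survivors spent 48 h on drug and deaths came at 96 h, the difference would be 0.1445 × (96 − 48) = +6.9 h.

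**The +35 h is all mortality.** This is correct: drug duration in survivors was set equal. The figure shows how far the scoring rule moves the result, not an effect on vasoactive need.

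**Hidden harm.** A reader might fear that excess deaths would go unseen. The SAP tests 28-day and 90-day mortality and adds survival analysis, so they would show there. Only this outcome would mislead.

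**Other rules are defensible.** This also stands. Zero gives a day-1 death and a day-13 death the same score. Counting hours alive and off drug without the zero is reasonable and gives similar results here: with every death at 48 h off drug for its last 14.4 h, the difference is 0.1445 × (240 − 14.4) = +32.6 h. The need is for one stated rule.

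**Conclusion.** The omission is certain from the text. It is more than missing detail, because a literal count credits hours after death and so removes the mortality-driven difference: from +25 to +45 h with deaths scored 0, to between about −13 and +5 h. That loss holds across the ranges tried. Reversal is small and occurs only if patients who die have fewer hours on drug than survivors.

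The sizes are illustrative. They rest on the plan's mortality rates taken as 28-day risks and on assumed early-death share, survivor drug time and time to death. This is a secondary outcome; the primary mortality analysis and the 152/168 patients do not depend on it. It should be corrected, but it does not threaten the trial's main conclusion.

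**What to change.** In the protocol's outcome definition and in the SAP:

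- Define the outcome as hours alive and free of vasoactive drugs from randomisation to day 14, with death on or before day 14 scored 0 (worst rank).
- State that LOCF is not applied to deaths for this outcome.
- Name one rank-based test as its primary test. Stratifying by centre is optional and a separate matter from the death rule.
- Report 14-day deaths and time on drug in survivors, by arm, beside the score.

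The cost is a few sentences and no new data, provided the time of death and the start and stop times of vasoactive drugs are recorded. The small downside is that the score mixes death with drug duration, so it cannot be interpreted without its components.
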